1.3 Preclinical Studies Supporting the Safety of VRC-EBOADC086-00-VP (cAd3-EBO S)

Prior to evaluation as an Ebola antigen vector, cAd3 underwent nonclinical toxicology evaluations as both an investigational HCV vaccine product, AdCh3-HCV (BB-IND 14818, Okairos, Inc.) and an investigational HIV vaccine product, VRC-HIVADC064-00-VP. In addition, DNA plasmid vaccines expressing the Ebolavirus Zaire or the Sudan DNA WT GP antigens have been evaluated in both a GLP toxicity study and two Phase I clinical trials (BB-IND 13609, RCHSPB). The March 2014 Ebola outbreak in West Africa [34] prompted the VRC/NIAID to accelerate evaluation of VRC-cAd3-EBO [EBOADC069-00-VP – a mix of two vectors - one expressing the WT GP Zaire and one expressing the WT GP Sudan]; and the VRC/NIAID proposed to the FDA that the prior, related nonclinical and clinical studies (AdCH3-HCV, cAd3-HIV, Ebola DNA WT GP) supported evaluation of the cAd3-EBO vaccine through a staged, dose escalation Phase I study design without the conduct of a GLP toxicity study. The FDA concurred and no preclinical GLP toxicology study was performed prior to phase I initiation. The VRC/NIAID with its collaborating researchers then sought and received approval to evaluate the cAd3 EBO WT GP Zaire vaccine alone as a vaccine under the same

IND. This was designated VRC-EBOADC076-00-VP (cAd3-EBO Z). The current proposal is now to re-evaluate the other component of cAd3-EBO, cAd3-EBO S as a separate vaccine with the same staged, dose escalation Phase I study design.

1.4 Nonclinical Immunogenicity and Protection Studies of cAd3 Constructs

Several non-GLP studies were performed in cynomolgus macaques to select the cAd3-based EBO constructs for further development and to provide animal proof-of-concept data before the Phase I clinical studies. Research-grade materials, made with the same constructs as clinical material, of 1) cAd3 EBO Z (containing GP from Ebolavirus Zaire), 2) cAd3 EBO S (containing WT GP from Ebolavirus Sudan), 3) cAd3-EBO (composed of a 1:1 ratio of cAd3 EBO Z and cAd3 EBO S) [18] were used in all respective viral challenge studies summarized below in Table 3.

Table 3. Preclinical Proof-of-Concept Studies in Cynomolgus Macaques

Study Purpose	Study Outcome
Demonstrate protection against lethal challenge with Ebolavirus Zaire in cynomolgus macaques after single IM dose of cAd3-EBO Z	100% protection after a single IM dose of cAd3-EBO Z at 10^{10} and 10^{11} VP
Demonstrate protection against lethal challenge with Ebolavirus Zaire in cynomolgus macaques after single IM dose of cAd3-EBO	100% protection after a single IM dose of cAd3-EBO at 2×10^{10} VP 50% protection after cAd3-EBO at 2×10^9 VP
Demonstrate protection against lethal challenge with Ebolavirus Sudan in cynomolgus macaques after single IM dose of cAd3-EBO	100% protection against Ebolavirus Sudan after a single IM dose of cAd3-EBO at 2×10^{10} VP
Demonstrate generation of humoral and cellular immune responses after single IM dose of cAd3-EBO at 2×10^9 or 2×10^{10} VP	Single IM dose of cAd3-EBO at 2×10^9 VP or 2×10^{10} VP elicited antibody and antigen-specific CD4+ and CD8+ T cell responses. The lower cellular immune responses correlated with the lower level of protection (50%) observed after the 2×10^9 VP dose.
Demonstrate durability of the immune responses after single IM dose of cAd3-EBO Z at 10^{11} VP or cAd3-EBO at 2×10^{10} VP administered 10 months before the lethal challenge with Ebolavirus Zaire.	Protective immune responses measured during the acute phase of infection declined over time. When challenged 10 months after vaccination, 2/4 macaques were protected after a single IM dose of cAd3-EBO Z at 10^{11} VP while 0/4 were protected after a single IM dose of cAd3-EBO at 2×10^{10} VP.


Demonstrate protection against lethal challenge with Ebolavirus Zaire in cynomolgus macaques after prime with single IM dose of cAd3-EBO and week 8 boost with single IM dose of MVA (expressing GPs from EBOV and SUDV)
	
100% protection after a prime with a single IM dose of cAd3-EBO at 10^{10} VP and week 8 boost with a single IM dose of MVA (expressing GPs from EBOV and SUDV) at 10^8 PFU**

Demonstrate immunogenicity and protection against lethal IM or aerosol challenge with Ebolavirus Sudan in cynomolgus macaques after single IM dose of cAd3-EBO S
	
100% protection against IM challenge with Ebolavirus Sudan after a single IM dose of cAd3-EBO S at 10^{10} VP; 4 of 5 animals survived aerosol challenge after a single IM dose of cAd3-EBO S at 10^{10}VP. Pre-challenge plasma anti-GP titers were comparable in both groups of animals.

*VP – Viral Particles **PFU – Plaque forming units = A measure of the quantity of individual infectious particles (e.g. virus particles) based on the number of plaque formed per unit volume.
	

1.5 Dose Justification for cAd3-EBO S

Quantification of the vaccine is based on cAd3 particle units (PU). The cAd3-EBO S vaccine will be evaluated in humans at 1×10^{10} PU and 1×10^{11} PU doses. These doses were selected based on a good safety profile, ease of administration, and reliable immunogenicity from data collected in non-human primate studies. In addition, the doses were shown to provide partial to full protection in the accepted challenge model. Doses between 1×10^{10} PU and 1×10^{11} PU demonstrated Ebola-Sudan GP-elicited immunogenicity was also comparable to that seen to the Ebola-Zaire and Marburg GP antigens when expressed by the same cAd3 vector. The doses of cAd3 vector proposed for this study, when expressing a variety of viral inserts, have also been demonstrated to be safe in humans. Please refer to the IB for additional details.

2.0 STUDY OBJECTIVES

2.1 Primary Objectives

- To evaluate the safety and tolerability of VRC-EBOADC086-00-VP when administered IM at a dose of 1×10^{10} particle units (PU) to healthy adults;
- To evaluate the safety and tolerability of VRC-EBOADC086-00-VP when administered IM at a dose of 1×10^{11} PU to healthy adults.

2.2 Secondary Objectives

- To evaluate the antibody response to the GP insert and the cAd3 vector in VRC-EBOADC086-00-VP at 4 weeks after vaccination as assessed by GP ELISA and vector-specific neutralization assays, respectively.
- To evaluate the Ebola Sudan GP-specific T cell responses in VRC-EBOADC086-00-VP at 4 weeks after vaccination as assessed by ICS.

2.3 Exploratory Objectives

- To evaluate the immunogenicity of VRC-EBOADC086-00-VP by various assay methods at some or all of the research sample collection time points indicated in the SOE; genetic factors associated with immune response may also be evaluated.
- To evaluate vaccine-induced mRNA expression profiles through Study Week 1.
- To evaluate the time course and durability of cAd3 neutralizing antibody titers, mediators of inflammation following vaccination and time course and durability of immune response by a variety of exploratory assays using samples collected throughout the study.
- To isolate MAbs to determine epitope specificity and their functional capacity.

3.0 ENDPOINTS

3.1 Primary Endpoints: Safety

Assessment of product safety will include clinical observation and monitoring of clinical chemistry and hematology parameters. Safety will be closely monitored after injection and evaluated through 48 weeks after the study injection. The following parameters will be assessed:

- Occurrence of solicited local reactogenicity signs and symptoms for 7 days following the vaccination
- Occurrence of solicited systemic reactogenicity signs and symptoms for 7 days following the vaccination
- Change from baseline for safety laboratory measures
- Occurrence of adverse events of all severities through 28 days after the study injection
- Occurrence of serious adverse events and new chronic medical conditions through the last study visit

3.2 Secondary Endpoints: Immunogenicity

Antibody titers, response rates and magnitudes will be the immunogenicity endpoints for the following assays where relevant: ELISA and neutralization antigen-specific assays for antibody responses and ICS assays for T cell responses. The principal time point for assessing antibody and T cell responses is Week 4 after vaccination.

3.3 Exploratory Endpoints

ELISpot assays to assess T and B cell responses will be performed with research samples collected at study timepoints shown in the SOE (Appendix 1), as well as evaluation of genetic factors associated with immune responses and time courses of immune responses (i.e. AUC evaluation) may be completed as exploratory evaluations. MAbs may be isolated from cryopreserved peripheral blood mononuclear cells (PBMC) and evaluated to determine among other characteristics, epitope specificity, and functional capacity. Vaccine-induced mRNA expression profiles through 1 week after vaccination may also be performed as an exploratory evaluation. Plasmablasts will be isolated from whole blood at day 7 to evaluate immediate development of antibodies to Ebola GP.

4.0 STUDY DESIGN AND POPULATION

This is a Phase I open-label, dose-escalation clinical trial to evaluate the safety, tolerability and immunogenicity of a recombinant vector for the Sudan strain of the Ebola virus. This study will be conducted at the MUWRP in Kampala, Uganda.

A total of 40 healthy adults, 20 in each dosage group, will receive a single vaccine injection of cAd3-EBO S at 1×10^{11} PU/mL or 1×10^{10} PU/mL. The study will begin with enrollment of 3 participants into Group 1. After at least 7 days of follow-up for the first 3 vaccinated participants, an interim safety review will occur before enrollment of additional participants into the group. If no safety issues are identified, an additional 17 participants will be enrolled to complete Group 1. When there is a minimum of seven days of follow-up safety data from the last enrolled participant in Group 1, an interim safety review will occur. Once no safety issues are identified, enrollment of participants into the next dose level will begin with the enrollment of 3 participants. After at least 7 days of follow-up for the first 3 vaccinated participants in Group 2, an interim safety review will occur before enrollment of additional participants into Group 2. If no safety issues are identified, an additional 17 participants will be enrolled to complete Group 2. For the first 3 participants in each group, only one participant per day will be enrolled. The study groups and vaccination schema is shown in Table 1.

Study agent administration will be on Day 0. The study includes daily review of any new safety data by a study clinician and weekly review of safety data by the Protocol Safety Review Team (PSRT). The staged enrollment plan and plan for interim safety reviews (Section 7.3) applies to both Group 1 and Group 2. The interim safety reviews will be conducted by the PSRT.

4.1 Eligibility

Screening for eligible volunteers will be performed within 8 weeks before the first administration of study vaccine at Week 0. Study participants must be healthy (on the basis of medical history, physical examination, vital signs measurement, and laboratory assessments), adult men and women, aged 18 to 50 years.

4.1.1 Inclusion Criteria

A volunteer must meet all of the following criteria:

1. 18 to 50 years old.
2. Available for clinical follow-up through Week 48 after enrollment.
3. Able to provide proof of identity to the satisfaction of the study clinician completing the enrollment process.
4. Able and willing to provide fingerprints and have their photographs taken including injection site photographs.
5. Must allow home visits
6. Must complete an Assessment of Understanding (AoU) prior to enrollment by answering 9 out of 10 questions at least once in 3 attempts.

7. Able to read (English or Luganda) and willing to complete the informed consent process.
8. In good general health without clinically significant medical history.
9. Physical examination and laboratory results without clinically significant findings and a body mass index (BMI) ≤ 40 within the 56 days prior to enrollment.

Laboratory Criteria within 56 days prior to enrollment:

10. Hemoglobin ≥ 11.0 g/dL for women; ≥ 12.5 g/dL for men.
11. White blood cells (WBC) = 2,500-12,000 cells/mm³.
12. Total lymphocyte count ≥ 800 cells/mm³.
13. Platelets = 125,000 – 400,000/mm³.
14. Alanine aminotransferase (ALT) ≤ 1.25 x upper limit of normal.
15. Serum creatinine ≤ 1 x upper limit of normal.
16. HIV-uninfected as evidenced by a negative HIV diagnostic test.

Female-Specific Criteria:

17. Negative β -HCG (human chorionic gonadotropin) pregnancy test; serum β -HCG at screening and urine β -HCG at enrollment if woman is of reproductive potential.
18. Agrees to use an effective means of birth control from at least 21 days prior to enrollment through 24 weeks after study vaccination if assessed to be of reproductive potential.

4.1.2 Exclusion Criteria

A volunteer will be excluded if one or more of the following conditions apply:

Volunteer has received any of the following substances:

1. Investigational Ebola or Marburg vaccine in a prior clinical trial or prior receipt of a cAd3 adenoviral vectored investigational vaccine.
2. Chronic use of immunomodulators and systemic glucocorticoids in daily doses of glucocorticoid equivalence > 20 mg of prednisolone, for periods exceeding 10 days. Non-steroidal anti-inflammatory drugs [NSAIDS] are permitted. Participants that have used less than the stated glucocorticoid dose may still be excluded at the Investigator's discretion.
3. Blood products within 112 days (16 weeks) prior to enrollment.
4. Investigational research agents within 28 days (4 weeks) prior to enrollment.

5. Live attenuated vaccines within 28 days (4 weeks) prior to enrollment.
6. Subunit or killed vaccines within 14 days (2 weeks) prior to enrollment.
7. Current anti-tuberculosis prophylaxis or therapy.

Female-specific criteria:

8. Woman who is pregnant, breast-feeding or planning to become pregnant during the first 24 weeks after study vaccine administration.

Volunteer has a history of any of the following clinically significant conditions:

9. Serious adverse reactions to vaccines such as anaphylaxis, urticaria (hives), respiratory difficulty, angioedema, or abdominal pain.
10. Allergic reaction to excipients in the study vaccine including gentamycin, neomycin or streptomycin.
11. Clinically significant autoimmune disease or immunodeficiency.
12. Asthma that is not well controlled.
13. Positive result on an RPR test.
14. Diabetes mellitus (type I or II).
15. Thyroid disease that is not well controlled.
16. A history of hereditary angioedema (HAE), acquired angioedema (AAE), or idiopathic forms of angioedema.
17. Idiopathic urticaria within the last 1 year.
18. Hypertension that is not well controlled.
19. Bleeding disorder diagnosed by a doctor (e.g. factor deficiency, coagulopathy, or platelet disorder requiring special precautions) or significant bruising or bleeding difficulties with IM injections or blood draws.
20. A malignancy that is active, currently being treated, or not surgically cured.
21. Seizure in the past 3 years or treatment for seizure disorder in the past 3 years.
22. Asplenia or functional asplenia.
23. Psychiatric condition that precludes compliance with the protocol; past or present psychoses; or within five years prior to enrollment, history of a suicide plan or attempt.

24. Any medical, psychiatric, social condition, occupational reason or other responsibility that, in the judgment of the investigator, is a contraindication to protocol participation or impairs a volunteer's ability to give informed consent.

5.0 STUDY PROCEDURES

5.1 Schedule of Evaluations

Evaluation of the safety of this vaccine will include laboratory studies, medical history, physical assessment by clinicians, and participant self-assessment recorded on a 7-day diary card. The schedule of evaluation is located in Appendix 1. Total blood volume drawn from each participant will not exceed 450 mL in any 3-month period.

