7.3 Protocol Safety Review Team

The PSRT will review all AEs (including reportable AEs) on a regular and expedited basis as needed. In addition, the PSRT will review aggregate safety data reports on a weekly basis until 4 weeks after all participants have completed the vaccination, then the safety reviews will occur monthly. The PSRT will review SAEs that potentially meet study pause criteria on an expedited basis and will decide if the study should be paused for participant safety purposes. This team includes the following: PI or designee, Associate Investigators, Protocol Consultants, DoD Research Monitor, sponsor IND Medical Officer or designee, and other VRC Representatives. Additional participants could include study personnel and senior clinical research nursing staff. A quorum is established with the PI or designee, one AI or designee, one MHRP protocol consultant or their designee, and IND Medical Officer or their designee. If the DoD Research

Monitor is not available for the PSRT call, they must provide input by email and then be immediately emailed the outcome of the PSRT discussion.

In addition to the regular and expedited meetings, the PSRT will conduct the following three interim safety data reviews to assess whether or not the safety data meet criteria for moving on to the next stage of the study.

Review for Continuation of 1 x 10¹⁰ PU Dose of VRC-EBOAD086-00-VP: No more than 1 participant per day will be enrolled into the group for the first 3 participants. When the first 3 participants who have received the 1 x 10¹⁰ PU dose have completed post vaccination follow up through at least the “Study Day 7” visit, an interim safety data review will be conducted by the PSRT. Enrollment of the remaining 17 participants in the group may proceed if the PSRT assesses the data as safe to continue.

Review for Dose Escalation to 1 x 10¹¹ PU Dose of VRC-EBOAD086-00-VP: When the last participant who has received the 1 x 10¹⁰ PU dose has completed post vaccination follow up through at least the “Study Day 7” visit, an interim safety data review will be conducted by the PSRT. If the safety data support proceeding to the 1 x 10¹¹ dose, then enrollment of Group 2 will begin.

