APPENDIX 1: SCHEDULE OF EVALUATIONS

RV 508 Schedule of Evaluations												
Visit	01	02	02A	02B	02C	02D	03	04	05	06	07	
Week of Study	-8 to 0	W 0	W 1	W 1	W 1	W 2	W 4	W 8	W 16	W 24	W 48	
Day of Study	-56 to 0	D 0	D 1	D 3	D 7	D 14	D 28	D 56	D 112	D 168	D 336	
Clinical Evaluations	Screening ¹	Enrollment										
Informed Consent, Assessment of Understanding	X											
Physical exam and weight at screen; Vital signs, targeted exam at other visits	X	X		X	X	X	X	X	X	X	X	
Medical history for eligibility at screen; interim history other visits	X	X		X	X	X	X	X	X	X	X	
Study Vaccination ²		X										
Begin/Review 7-Day Diary Card ⁶		X		X	X							
Telephone contact; clinic visit if indicated			X									
Counseling on pregnancy prevention		X				X	X	X	X			
CBC w/total lymphocyte count	3	3		3	3	3	3	3		3		
Pregnancy test: urine (or serum) ³	X	X					X			X		
Creatinine and ALT	4	4		4	4	4	4	4				
HIV ⁵ and RPR	6											
Research Immunology												
Serum storage for antibody assays	12	12		12	12	12	12	12	12	12	12	
Pre-Existing Vector Immunity testing	X											
PBMC and plasma for storage	8.5	68			59.5	42.5	59.5	42.5	59.5	76.5	76.5	
Intracellular RNA		3		6	6							
HLA type ⁴									17			
Daily Volume (mL)	33.5	90	0	25	77.5	61.5	78.5	61.5	88.5	91.5	88.5	
Max. Cumulative Volume (mL)	33.5	123.5	123.5	148.5	226	287.5	366	427.5	516	607.5	696	

Visit windows: 02A (+1 day); 02B (+2 days); 02C (+3 days); Visit 02D (± 3 days); Visits 03 and 04 (± 7 days); Visits 05, 06 and 07 (± 14 days).

¹ Most screening evaluations must be no more than 56 days prior to Day 0 to be used for eligibility (pregnancy test from Day 0 must be used for eligibility). If clinical assessment on Day 0 suggests significant changes may have occurred since screening, then physical examination & laboratory studies done on Day 0 are used for eligibility.

Day 0 = day of enrollment and vaccine injection. Day 0 evaluations prior to first injection are the baseline for assessing adverse events subsequently.

² Complete post vaccination vitals and injection site assessment after the study injection (target to complete this within the interval 30 to 45 minutes post-vaccination). Subjects must remain in the clinic for at least 30 to 60 minutes after injection.

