³ Negative pregnancy test results must be confirmed for women of reproductive potential prior to administering the vaccine injection. Serum pregnancy testing at screening visit, urine pregnancy testing at enrollment visit and all follow-up visits where indicated. Serum taken from blood collected for HIV and RPR tests.

⁴ HLA type blood sample is collected once at any time point in the study and is shown as a Visit 05 evaluation for convenience; however, if HLA type is already available in the medical record it does not need to be repeated. HLA type may also be obtained from a frozen sample.

⁵ Includes pre/post-test counseling as per site SOP

⁶ The Diary Card can be collected at any time between Visit 02C and Visit 02D (to include at an unscheduled visit) in order to obtain a complete day 7 assessment of any solicited symptoms.

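### Appendix 1 omits 7 mL of Day 7 safety labs from its blood volume totals, so a permitted early HLA draw can pass the 450 mL cap by 1.5 mL while appearing compliant

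*Combined protocol and SAP*

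**What the plan says.** Section 5.1 refers the reader to Appendix 1 for the schedule and states the limit: "Total blood volume drawn from each participant will not exceed 450 mL in any 3-month period".

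Appendix 1 gives the volume of each sample at each visit. The main rows are:

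- "CBC w/total lymphocyte count 3 3 3 3 3 3 3 3"
- "Creatinine and ALT 4 4 4 4 4 4 4"
- "Serum storage for antibody assays 12 12 12 12 12 12 12 12 12 12"
- "PBMC and plasma for storage 8.5 68 59.5 42.5 59.5 42.5 59.5 76.5 76.5"

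It also lists 6 mL for HIV and RPR at screening, intracellular RNA (3 mL on Day 0, 6 mL on each of Days 3 and 7) and 17 mL for HLA typing, shown at Visit 05 (Week 16). The daily totals are printed as "Daily Volume (mL) 33.5 90 0 25 77.5 61.5 78.5 61.5 88.5 91.5 88.5", and a cumulative row follows that ends at 696 mL.

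Footnote 4 makes the HLA timing flexible: "HLA type blood sample is collected once at any time point in the study". It explains that the Visit 05 placement is only a convenience. No new draw is needed if the type is already on record, and a frozen sample may be used.

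**The concern.** The fifth daily total, 77.5 mL at Visit 02C (Day 7), is smaller than the sum of the samples listed in that column. The cumulative row is built from the daily row, so the shortfall carries through to the end of the study.

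A site or ethics committee would use these rows to decide whether a participant is within 450 mL. The scheduled plan stays inside the limit either way. The difficulty is the HLA sample: its 17 mL fits the margin the printed table shows, but not the margin the itemised draws leave. A site that relied on the printed rows could move the draw forward, as footnote 4 allows, and exceed the protocol's own limit without knowing it.

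**Working it through.** **Inputs.** All volumes are from Appendix 1, in mL. The cap of 450 mL is from Section 5.1.

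**Step 1: reproduce the printed cumulative row.** Adding the printed daily volumes in order gives 33.5, 123.5, 123.5, 148.5, 226, 287.5, 366, 427.5, 516, 607.5, 696. Every printed cumulative figure is reproduced, so that row contains no separate error.

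**Step 2: rebuild each daily volume from its samples.**

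| Visit (day) | Samples | Sum | Printed | Corrected cumulative | Printed cumulative |
|---|---|---|---|---|---|
| 01 (screening) | 3 + 4 + 6 + 12 + 8.5 | 33.5 | 33.5 | 33.5 | 33.5 |
| 02 (D0) | 3 + 4 + 12 + 68 + 3 | 90 | 90 | 123.5 | 123.5 |
| 02A (D1) | none | 0 | 0 | 123.5 | 123.5 |
| 02B (D3) | 3 + 4 + 12 + 6 | 25 | 25 | 148.5 | 148.5 |
| **02C (D7)** | **3 + 4 + 12 + 59.5 + 6** | **84.5** | **77.5** | **233** | **226** |
| 02D (D14) | 3 + 4 + 12 + 42.5 | 61.5 | 61.5 | 294.5 | 287.5 |
| 03 (D28) | 3 + 4 + 12 + 59.5 | 78.5 | 78.5 | 373 | 366 |
| 04 (D56) | 3 + 4 + 12 + 42.5 | 61.5 | 61.5 | 434.5 | 427.5 |
| 05 (D112) | 12 + 59.5 + 17 | 88.5 | 88.5 | 523 | 516 |
| 06 (D168) | 3 + 12 + 76.5 | 91.5 | 91.5 | 614.5 | 607.5 |
| 07 (D336) | 12 + 76.5 | 88.5 | 88.5 | 703 | 696 |

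Ten of the eleven columns agree exactly. Visit 02C is short by 84.5 − 77.5 = 7 mL. The printed 77.5 is what remains when CBC (3) and creatinine/ALT (4) are left out: 12 + 59.5 + 6 = 77.5.

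**Step 3: could the table have been misread?** The CBC row has eight entries, but the printed daily totals account for only seven. The creatinine/ALT row has seven, and the totals account for six. If the unused entry in either row belonged to another visit, that visit's sum would no longer match its printed total. No other column has room for either entry.

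**Step 4: compare with the cap, screening through Week 8.**

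- Printed: 427.5 mL, margin 450 − 427.5 = 22.5 mL.
- Itemised: 434.5 mL, margin 450 − 434.5 = 15.5 mL.
- Printed plus HLA: 427.5 + 17 = 444.5 mL, under the cap.
- Itemised plus HLA: 434.5 + 17 = 451.5 mL, over by 1.5 mL.

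**Step 5: when do these draws share one 3-month window?** The protocol does not define 3 months in days. Taking 91 days, the earliest screening day in the same window as the Week 8 visit is:

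- Week 8 on Day 56: 91 − 56 = 35 days before Day 0.
- Week 8 on Day 49 (early end of the ±7-day window): 91 − 49 = 42 days before.
- Week 8 on Day 63 (late end): 91 − 63 = 28 days before.

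Using 90 or 92 days shifts each limit by one day. Screening may take place up to 56 days before Day 0, so some participants will fall inside the window and others may not. For those outside it, Day 0 to Week 8 is 434.5 − 33.5 = 401 mL, or 401 + 17 = 418 mL with HLA, within the cap.

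**Step 6: HLA left at Visit 05.** The earliest Visit 05 is Day 112 − 14 = Day 98. A 91-day window ending there starts on Day 7, and its draws total 84.5 + 61.5 + 78.5 + 61.5 + 88.5 = 374.5 mL, well inside the cap.

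**The case against.** The addition error itself is hard to dispute. The case on the other side concerns what follows from it.

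- **The schedule as shown does not breach the cap.** This stands. Exceeding 450 mL requires a fresh HLA draw, taken by Week 8, in someone screened close enough to Day 0. The excess is then 1.5 mL, about 0.3% of the limit, and no clinical harm is claimed.
- **The protocol already has ways to comply.** The cap governs whatever footnote 4 permits, and HLA type can come from an existing record or a frozen sample. This also stands, but a site can apply the cap correctly only if the totals it consults are right. Here they give the wrong answer for a permitted draw.
- **The two lab entries, rather than the total, could be the mistake.** If no Day 7 CBC or creatinine/ALT was intended, the printed totals hold and an early HLA draw gives 444.5 mL. Section 7.3 requires follow-up through at least the Day 7 visit before "an interim safety data review will be conducted by the PSRT", but it does not name these tests, and Appendix 3 lists only a blood draw that day. The printed schedule does include both tests, however, and Section 3.1 makes laboratory change from baseline a primary safety parameter. Keeping the tests is the better reading, and the sponsor should confirm it. On either reading the table contradicts itself.
- **Barring early HLA draws is broader than needed,** because participants with screening outside the window would reach only 418 mL. That is fair, but one fixed rule is simpler than a rolling calculation for each participant, and little is lost.

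**Conclusion.** The concern holds. Appendix 1 understates the Day 7 volume by 7 mL (84.5 mL against 77.5 mL printed), and all seven cumulative figures from Day 7 to Week 48 are low by the same amount. The scheduled plan remains within 450 mL, with a screening-to-Week-8 total of 434.5 mL and a margin of 15.5 mL.

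The practical consequence is conditional. A fresh 17 mL HLA draw by Week 8 brings the total to 451.5 mL when screening falls in the same 3-month window. That means screening within about 5 weeks of Day 0, taking 3 months as 91 days and Week 8 on Day 56, or 28 to 42 days across the Week 8 visit window. The result assumes that the Day 7 safety labs are intended, as the table shows. It does not rely on repeat tests, which would add further volume. This is a minor correction with no bearing on endpoints or analyses.

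**What to change.** In Appendix 1, change the Visit 02C daily volume to 84.5 mL and the cumulative row from Visit 02C onward to 233, 294.5, 373, 434.5, 523, 614.5 and 703 mL. The sponsor should confirm that the Day 7 CBC and creatinine/ALT are intended. They should be kept unless there is a reason to drop them, because the staged enrolment reviews look at follow-up through that visit.

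Amend footnote 4 so that a fresh HLA draw is taken at Visit 05 or later, with an existing result or a frozen sample used if the type is needed sooner. If the sponsor prefers to keep the flexibility, the footnote could instead require the site to check the participant's rolling 3-month total against the corrected rows before moving the draw.

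The cost is eight table cells and one footnote clause, with no change to visits, endpoints or analyses.
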